## 2 STUDY OBJECTIVES AND THEORY OF CHANGE

The **goal** of this study is to mitigate AMR using a novel dynamic ePOCT+ tool that helps front-line HWs manage sick patients, enhanced by additional digital platforms to promote uptake, sustainability, and integration of the tool into the health system. More specifically, this study seeks to:

### 2.1 Objective 1

**Improve the integrated management of children with an acute illness** (more specific and diverse diagnoses; reduced antibiotic prescriptions) through the provision of an electronic CDSA (ePOCT+) to clinicians working at primary care level.

*Hypothesis 1:* The use of ePOCT+ in the outpatient PHC setting in Rwanda will result in decreased prescription of antibiotics while maintaining similar clinical outcomes.

*Hypothesis 2:* The use of ePOCT+ in the outpatient PHC setting in Rwanda will result in improved quality of care.

### 2.2 Objective 2

**Improve the diagnostic and prognostic accuracy of the clinical algorithm across spatiotemporal variations in epidemiology and resources** through machine learning analyses of the data generated through the ePOCT+ tool, checked by clinical experts.

*Hypothesis 3:* Modifications in the electronic CDSA based on the results of ML analyses will enable similar or better outcomes over the course of the study despite temporal and spatial variability in disease patterns and/or availability of resources.

### 2.3 Objective 3

**Enhance the health management information system for monitoring and evaluation and supportive supervision** (increased number of meaningful indicators that are reviewed and actioned regularly) through additional data analysis and visualization of patient-level data generated by the ePOCT+ tool.

*Hypothesis 4:* The patient-level clinical data that is visualized and analyzed in near real-time will lead to improved ability of the DHMT to monitor the quality of patient care and undertake targeted supportive supervision of HFs and HWs.

*Hypothesis 5:* The patient-level clinical data that is visualized and analyzed in near real-time will lead to a more accurate epidemiological profile of the district and improved spatial and temporal resource allocation.

### 2.4 Objective 4

[figure not shown]
**Create a framework for the implementation of dynamic clinical decision support algorithms and supporting tools**, for large-scale, sustainable, and clinically responsible use of machine learning and data science in digital health.

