## 9 STATISTICAL METHODS

### 9.1 Sample size calculations

For the parallel cluster study in Phase 1, the primary analysis will evaluate whether the use of ePOCT+ for case management of sick children in PHC facilities results in decreased antibiotic prescriptions (superiority analysis) at the initial consultation. Superiority in antibiotic prescription is defined as a relative decrease of  $\geq 25\%$  in the proportion of children prescribed an antibiotic. We estimated a cluster size of 660 patients (monthly utilization of 220 – accounting for up to 30% non-adherence from 315 – over 3 months) and an intraclass correlation coefficient of 0.025. Non-adherence here is defined as HWs not using the application for all eligible patients that come to the HF for various reasons. To have 80% power to detect a 25% reduction in antibiotic prescription (e.g. from 35% to 26%), for a one-sided hypothesis test at alpha of 0.05, we would require a minimum of 11 clusters per arm. With 16 clusters (or HF) over 3 months, we expect a total of 10,500 participants per arm, this sample size is

sufficient to test for non-inferiority in the secondary outcome (clinical cure at day 7) between the control and intervention groups.

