4.2 Analysis population definitions

Intention-to-treat population: This population includes all patients enrolled in the study, regardless of whether the HW used ePOCT+ (intervention arm), or entered the final treatment data in the eCRF (both arms).

Per-protocol population: This population only includes patients enrolled in the study for whom the clinician confirmed the final treatment (or absence of treatment) / referral status within the ePOCT+ tool (intervention arm) or in the eCRF (control arm).

Complete case set: All enrolled subjects (intervention or control) for whom day 7 clinical cure data was collected (i.e. excluding lost to follow-up patients).

Complete consultation set: All enrolled subjects (intervention or control) for whom at least information on treatments were collected at day 0.

5. Study population

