Effect modification of the primary outcome of antibiotic prescription will be performed in groups of patients where the highest reduction in antibiotic prescription is expected, and areas of extension of the content of the algorithm compared to the version tested in the previous ePOCT study. Effect modification by sex, age group (young infants ages 1 to 59 days, children aged 2 months to 5 years, and children aged 5 to 14 years), respiratory symptoms, fever without clinical source, gastrointestinal complaints (vomiting and diarrhea), skin problems, ear, nose and throat problems, will be assessed by incorporating an interaction term between the treatment arm and the respective variable, acknowledging that power will be low. Furthermore in order to adjust for potential imbalances in baseline characteristics between study groups, relevant baseline characteristics will be included as fixed effect variables in the final model. Baseline characteristic imbalance will be determined by statistical method (i.e., comparisons of treatment arms over all clusters and within clusters) and by consensus among the study analysis team.

The number of children lost to follow up may be quite high due to the difficult nature of phone follow-up at day 7, as found in previous studies with day 7 phone call lost to follow up rates of 13-25% (Christie et al., 2018; Hannigan, Chisale, Drew, Watson, & Gallagher, 2019; Nguhuni et al., 2017).

Comparatively, the proportion not cured at day 7 is expected to be quite low (3%). The use of a complete case analysis was therefore selected for the secondary outcome of day 7 clinical cure, as it would be the most conservative analysis. If we were to use the “enrolled set” and considered all day 7 lost to follow up as not being cured, this would dilute the difference between arms. Not considering lost to follow up cases as failures is also the approach used for similar studies with high number of LTF

and low proportion of outcomes (Källander et al., 2018). We may adjust the final model for further baseline variables (not already included as fixed effect variables) which are associated with missing outcome data (analogous to performing multiple imputation in the case of a single endpoint). As with the other fixed effect variables, baseline characteristic imbalances among patients lost to follow up will be determined by consensus among the study analysis team.

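### Complete-case analysis of day-7 cure is called the most conservative choice, which holds only under narrow conditions, and no sensitivity analysis for missing cure is planned

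*SAP*

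**What the plan says.** **Choice of analysis set.** SAP 6.1 states that a "complete case analysis was therefore selected for the secondary outcome of day 7 clinical cure, as it would be the most conservative analysis". SAP 4.2 defines the set as "All enrolled subjects (intervention or control) for whom day 7 clinical cure data was collected". The reasons given are that loss may be high, with earlier studies showing "day 7 phone call lost to follow up rates of 13-25" per cent, and that only 3% are expected not to be cured. The one alternative considered is to count every lost child as not cured. It is rejected because "this would dilute the difference between arms".

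**Provision for missing cure.** SAP 6.1 adds: "We may adjust the final model for further baseline variables", where these are associated with missing outcome data, and likens this to multiple imputation. Imbalances among lost children are to be settled by team consensus. The sensitivity analyses in Protocol 9.2 (intention-to-treat, per-protocol, complete case) are attached to the primary superiority analysis, not to cure.

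**Role of cure.** Hypothesis 1 in Protocol 2.1 expects "decreased prescription of antibiotics while maintaining similar clinical outcomes". Protocol 9.1 and the synopsis call the sample size "sufficient to test for non-inferiority in the secondary outcome (clinical cure at day 7) between the control and intervention groups". SAP 2.1.2 labels the same outcome as superiority. Neither document gives a margin.

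**The concern.** Whether an analysis is conservative depends on the question asked and on how the missing data arose. The SAP settles the matter by comparison with one other method and does not state the conditions.

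At stake is the statement that antibiotic use fell without worse outcomes. If loss differs between arms, or if lost children fare differently in the two arms, that statement describes only the children who were reached. Death, non-referred hospitalisation and unscheduled re-attendance come from the same day-7 contact (SAP 2.1.2), so they share the gap.

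Unequal loss is plausible. The trial is open-label (SAP 3.1) and facilities are assigned to arms on geographical grounds (SAP 3.2). Household mobile-phone ownership is 56% in Nyamasheke and 69% in Rusizi (Protocol Table 5), although the documents do not say that the arms divide by district.

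**Working it through.** **Inputs from the documents.** Loss L of 13–25% in earlier phone studies and 3% expected failure (SAP 6.1); 16 clusters of 660, about 10,500 per arm, and an intraclass correlation (ICC) of 0.025 for antibiotic prescription (SAP 3.3). **Assumptions.** Every split of loss between arms, every failure rate among lost children, any margin, and any ICC for cure.

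**1. Loss against failure.** 13/3 = 4.3 and 25/3 = 8.3.

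**2. The SAP's dilution argument.** With equal loss L, counting the lost as failures multiplies the difference by (1 − L). Take true failure of 3% and 5%, a 2.0-point difference:
- L = 13%: 0.87 × 2.0 = 1.74 points (odds ratio 1.70 falls to 1.13).
- L = 25%: 0.75 × 2.0 = 1.50 points (odds ratio 1.70 falls to 1.08).

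The argument is correct under equal, uninformative loss. For a no-harm question, complete case is then the stricter of the two. For superiority it is the less strict, because it keeps the larger difference.

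**3. The same comparison with unequal loss.** Take 3% failure among those reached in both arms, with 25% loss in the intervention arm and 13% in the control arm. Counting the lost as failures gives:
- Intervention: 0.75 × 3 + 25 = 27.25%.
- Control: 0.87 × 3 + 13 = 15.61%.

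That is an apparent harm of 11.64 points, where complete case shows none. If the two losses change places, so does the sign. Neither method is the conservative one in general.

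**4. What complete case can hide.** True failure in an arm = (1 − L) × 3% + L × f, where f is failure among the lost. Complete case shows a zero difference in each row.

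| Loss, intervention / control | f, intervention / control | Hidden difference |
|---|---|---|
| 25% / 13% | 10% / 10% | 4.75 − 3.91 = 0.84 points |
| 25% / 13% | 6% / 6% | 3.75 − 3.39 = 0.36 points |
| 20% / 20% | 5-point gap | 0.20 × 5 = 1.00 point |

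**5. Counts.** 16 × 660 = 10,560, which the SAP gives as 10,500. If that figure is before day-7 loss, 0.13 × 10,500 = 1,365 to 0.25 × 10,500 = 2,625 children per arm are lost. Observed failures would be 0.03 × 9,135 = 274 to 0.03 × 7,875 = 236.

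**6. What a tipping-point table would show.** Suppose 3% failure among those reached in both arms and equal loss L, with lost control children also failing at 3%. A non-inferiority finding at margin M reverses when failure among lost intervention children exceeds 3% + (M − h)/L. Here h = 1.96 × √(2 × 0.03 × 0.97 × D/n), n = 16 × 660 × (1 − L), D = 1 + (660 × (1 − L) − 1) × ICC, and h is held at its complete-case value. Example: L = 13%, ICC 0, M = 2 points gives h = 0.493 points and 3 + 1.507/0.13 = 14.6%.

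| Assumed ICC for cure | Assumed margin | L = 13% | L = 25% |
|---|---|---|---|
| 0 | 1 / 2 / 3 points | 6.9 / 14.6 / 22.3% | 4.9 / 8.9 / 12.9% |
| 0.01 | 1 / 2 / 3 points | not met / 8.5 / 16.2% | not met / 5.8 / 9.8% |
| 0.025 | 1 / 2 / 3 points | not met / 3.5 / 11.2% | not met / 3.2 / 7.2% |

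*Not met*: the complete-case interval already crosses the margin.

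**The case against.** The SAP's reasoning is sound against the comparator it names. With equal loss, counting the lost as failures pulls the arms together and makes no harm easier to conclude; step 2 confirms this. A reader might infer that complete case is the wrong main analysis, or that it is never conservative for a no-harm aim. The documents do not support that.

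Nor is 13–25% a forecast for this trial. It comes from earlier phone studies, whereas this trial has a 6–14 day window, repeat calls and home visits. The help is partial: Protocol 8.1.6 describes home visits for caregivers without a phone or number, while an unanswered first call leads to up to four more attempts and then loss.

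A reader might also infer that harm among lost children would go unseen. That is too strong. The flowchart shows follow-up by arm and block (Protocol 9.2), missing data on important secondary endpoints are reviewed (Protocol 11.3), day-0 referral is recorded in both arms (Protocol 8.1.2), and visits to participating facilities can be linked (Protocol 8.1.3). Unequal loss would therefore be visible. Its effect on the cure comparison would not be quantified, and visits elsewhere would not be captured. That admitted or deceased children are harder to reach is plausible but not documented.

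Finally, the SAP's adjustment resembles imputation. It is optional, however, and valid only if loss is ignorable given few baseline variables, since clinical signs and comorbidities are not systematically collected (SAP 5.4).

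**Conclusion.** The point stands and the plan should be changed. The superlative fails on either label. For superiority, avoiding dilution is the less conservative choice. For no harm, complete case is stricter than the one alternative only if loss is similar between arms and unrelated to outcome. Nothing is pre-specified to test that condition for cure.

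The illustrated hidden differences are 0.36 to 1 point on a 3% base. They rest entirely on assumed loss splits and failure rates among the lost. Without a margin, the documents cannot show whether they are material.

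A reader might take 1,365–2,625 lost children per arm as expected numbers. They apply only if 10,500 is before day-7 loss, and this is unclear. SAP 3.3 includes loss to follow-up in the 30% allowance behind that figure; Protocol 9.1 describes the allowance as non-adherence only. The ratio of the loss rate to the failure rate does not depend on this.

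**What to change.** In SAP 6.1:

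- Delete the description of complete case as most conservative, and state the condition under which it is unbiased. Keep it as the main estimate.
- Report loss to follow-up by arm and facility.
- Pre-specify a tipping-point table over failure rates among the lost, varied separately in each arm. This is the part that addresses informative loss.
- Add a supporting multiple imputation by arm that respects facility clustering. Use data already on the tablet: age, main complaint, day-0 referral, antibiotic given and recorded re-attendance. It still assumes ignorable loss, but uses more than baseline variables.
- Reconcile the superiority label in SAP 2.1.2 with the protocol's non-inferiority wording and, if non-inferiority is kept, state the margin. The tipping-point table cannot be read against a no-harm claim without one.

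The cost is SAP wording and a little extra analysis on data already collected. The downside is that the conclusion of similar outcomes may become less firm.

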6.2 Exploratory analyses

Unless specifically described, the following analyses will be analyzed similarly to the binary secondary outcomes, using a random effects logistic regression model with the cluster (health facility) and patient included as a random effect.

- % of children hospitalized among those referred for hospitalization during an initial consultation

Timing and method of measurement: Hospitalization determined by day 7 (6-14) phone call or home visit. Referral for hospitalization as determined by eCRF during the initial consultation.

- % of children referred for malnutrition management during the initial consultation

Timing and method of measurement: Referred for malnutrition as documented in eCRF during the initial consultation.

- % of children referred for or performed at the health facility tuberculosis screening during the initial consultation

Timing and method of measurement: As documented in the eCRF during the initial consultation.

- % of children tested for HIV during the initial consultation:

Timing and method of measurement: As documented in the eCRF during the initial consultation.

- % of children tested for any laboratory test during the initial consultation:

Timing and method of measurement: As documented in the eCRF during the initial consultation

- % of clinicians accepting the ePOCT+ testing, treatment, diagnosis, and management recommendations during the initial consultation

Timing and method of measurement: As documented in the eCRF of the intervention arm (ePOCT+) during the initial consultation

- % of children/caretakers seeking additional medications after the initial consultation

Timing and method of measurement: Asking caretakers if they procured additional medications for their child after the initial consultation by phone call or home visit at day 7 (6-14)

- Change in % of children with antibiotic prescribed over time / across three cluster studies

Timing and method of measurement: Antibiotic prescription as documented in the eCRF (control arm) / ePOCT+ tool (intervention) during the initial visit (day 0).

Analysis: Compare change in percentage of prescription from month to month, and across the three cluster studies for the intervention arm and the control arm, using the control arm as comparison to correct for seasonality, and presenting implementation team mentorship visits and combined implementation team and DHMT mentorship visits to contextualize changes. Independent sample t-test will be used to compare change in antibiotic prescription between intervention and control arms.

- Change in % of children with basic anthropometrics and clinical signs assessed over time / across three cluster studies (intervention arm only)

Timing and method of measurement: Measurement and documentation of individual basic measurements (height, MUAC, Temperature), and clinical signs (respiratory rate) as documented within the ePOCT+ tool during the initial assessment (Day 0).

Analysis: Descriptive statistics presenting change in documentation of basic measurements and clinical signs from month to month, and across three cluster studies. Dates of implementation team mentorship visits and combined/supervised implementation team and DHMT mentorship visits and any changes in

implementation strategy will also be presented to contextualize the changes. Subgroup analyses may be conducted for each intervention health facility.

- Change in % of cases managed using ePOCT+ over time / across three cluster studies (intervention arm only):

Timing and method of measurement: Uptake of ePOCT+ is defined as the use of the ePOCT+ tool to guide the clinical consultation including the decision on what treatment to prescribe during the initial consultation (Day 0).

Analysis: Descriptive statistics to present change in the proportion of HWs' uptake from month to month, and across the three cluster studies will be presented. Dates of implementation team mentorship visits and combined/supervised implementation team and DHMT mentorship visits and any changes in implementation strategy will also be presented to contextualize the changes. Subgroup analyses may be conducted for each intervention health facility.

- Prognostic value of individual or combined predictors during the initial consultation to predict clinical failure/cure, hospitalization for more than one night and mortality (intervention arm)

